## LIST OF ABBREVIATIONS

ALT	alanine transaminase (or serum glutamic-pyruvic transaminase)
ANC	absolute neutrophil count
Anti-HIV AB	Anti-human immunodeficiency virus antibody
AST	aspartate transaminase (or serum glutamic-oxaloacetic transaminase)
AUC	area under the time-concentration curve
AUC 0-t	area under the time-concentration curve from time 0 to the last measurable concentration
AUC 0-τ	area under the time-concentration curve over the dosing interval at steady-state
BP	blood pressure
BUN	blood urea nitrogen
CAS	chemical abstracts service
CBC	complete blood count
CFR	Code of Federal Regulations
Cl	clearance
CL/F	apparent total body clearance after extravascular administration
C max	maximum concentration
C min	minimum concentration at steady state
CRF	case report form
CTP	Child-Turcotte-Pugh
ECG	electrocardiogram
EC	Ethics Committee
FDA	Food and Drug Administration
GCP	Good Clinical Practice
GLP	Good Laboratory Practice
HBsAg	hepatitis B surface antigen
HERG	human-ether-a-go-go
HIV	human immunodeficiency virus
HCV	hepatitis C virus
ICH	International Conference on Harmonisation
IgM AB	immunoglobulin M antibody
IM	intramuscular
INR	international normalized ratio

IRB	Institutional Review Board
IU	international unit
IUPAC	International Union of Pure and Applied Chemistry
Kel	apparent first-order terminal elimination constant
IV	intravenous
LFTs	liver function tests
ms	millisecond
PCR	polymerase chain reaction
PD	pharmacodynamics
PK	pharmacokinetics
PO	per orum (by mouth)
rDNA	recombinant deoxyribonucleic acid
RNA	ribonucleic acid
SAE	serious adverse event
$t_{max}$	time to peak concentration
$t_{1/2}$	apparent elimination half life
SOC	standard of care
TSH	thyroid stimulating hormone
UA	urinalysis
ULN	upper limit of normal
USP	United States Pharmacopeia
$V_{area/F}$	apparent volume of distribution
WBC	white blood cell

## PROTOCOL SUMMARY

### Study Title

A Phase II, Open Label Pilot Study of the Safety, Tolerability Pharmacokinetic and Pharmacodynamic Activity of EBP-994 Given Orally in Subjects Chronically Infected with HDV

### Sponsor

Eiger BioPharmaceuticals, Inc. (United States)  
Sigma CRO. (Turkey)

### Study Objectives

The primary objectives of the study are to:

- Evaluate the safety and tolerability of 12 weeks of treatment with a 200 vs. 300 mg PO BID dose of EBP-994 in subjects chronically infected with HDV
- Evaluate the pharmacodynamic (PD) activity of a 200 vs. 300 mg PO BID dose of EBP-994 on HDV viral load
- Evaluate the pharmacokinetic (PK) activity of a 200 vs. 300 mg PO BID dose of EBP-994
- Evaluate the safety, tolerability, PK, and HDV viral load of a treatment up to 48 weeks with EBP-994 alone and in combination with Norvir® and/or Pegasys® in subjects chronically infected with HDV

### Study Design

This study is a phase II, randomized, open-label study up to 48 weeks of treatment with EBP-994 alone, or in combination with Norvir® and/or Pegasys® in subjects chronically infected with HDV genotype 1. The duration of the study for each subject will last approximately 11-55 weeks (up to three week screening period, 4-48 week treatment period and four week safety follow-up period. The duration of the entire study is anticipated to be approximately 45 months (first subject in to last subject out). The investigator is free to initiate licensed medications at any time point and decrease the dose of EBP-994 if deemed warranted for GI side effects.

This study will explore EBP-994 in four groups of treatments:

Group 1: EBP-994 (up to 600 mg daily dose) monotherapy

Group 2: EBP-994 (up to 200 mg daily dose) in combination with Norvir®

Group 3: EBP-994 (up to 600 mg daily dose) in combination with Pegasys®

Group 4: EBP-994 (up to 150 mg daily dose) in combination with Norvir® and Pegasys®

### **Study Population and Number of Subjects**

Up to 75 subjects chronically infected with HDV genotype 1 will be enrolled at a single study sites.

#### Inclusion Criteria

A subject may be included in this study if he/she meets all of the following criteria:

1. Males or females, 18 to 65 years of age who are diagnosed with HDV by PCR
2. Chronic hepatitis D infection, genotype 1, documented by a positive anti-HDV Ab test of at least 6 months duration and detectable HDV RNA by PCR within 3 months to study entry
3. Liver biopsy within the last two (2) years or consent of having a liver biopsy which can be done at the Screening Visit
4. Electrocardiogram (ECG) shows no acute ischemia or clinically significant abnormality and a QT/QTc interval <450 milliseconds using Bazett's correction: QTc = QT/RR0.5 (ICH Guidance E14 Clinical Evaluation of QT/QTc Interval Prolongation and Proarrhythmic Potential for Non-Antiarrhythmic Drugs)
5. Females of childbearing potential (intact uterus and within one year since the last menstrual period) should be non-lactating and have a negative serum pregnancy test. In addition, these subjects should agree to use one of the following acceptable birth control methods throughout the study:
  - a. abstinence
  - b. surgical sterilization (bilateral tubal ligation, hysterectomy, bilateral oophorectomy) six month minimum
  - c. IUD in place for at least three months
  - d. barrier methods (condom or diaphragm) with spermicide
  - e. surgical sterilization of the partner (vasectomy for six months)
  - f. hormonal contraceptives for at least three months prior to the first dose of study drug
6. Willing and able to comply with study procedures and provide written informed consent

#### Exclusion Criteria

A subject will be excluded from this study if he/she meets any of the following criteria:

1. Participation in a clinical trial with or use of any investigational agent within 30 days of Study Visit 1
2. Patients co-infected with HIV or HCV (if HCV RNA is positive)
3. Patients with screening tests positive for anti-HIV Ab
4. Active jaundice defined by total bilirubin >2.0 and known not to have Gilbert's disease

5. INR  $\geq 1.5$
6. Eating disorder or alcohol abuse within the past two years, excessive alcohol intake ( $>20$  g per day for females (1.5 standard alcohol drinks) or  $>30$  g per day for males (2.0 standard alcohol drinks) (a standard drink contains 14 g of alcohol: 12 oz of beer, 5 oz of wine or 1.5 oz of spirits) (1.0 fluid oz (US) = 29.57 mL) or if in the opinion of the investigator, an alcohol use pattern that will interfere with study conduct
7. Drug abuse within the last six months with the exception of cannabinoids and their derivatives
8. Patients with absolute neutrophil count (ANC)  $<1500$  cells/mm $^3$ ; platelet count  $<100,000$  cells/mm $^3$ ; hemoglobin  $<12$  g/dL for women and  $<13$  g/dL for men; abnormal TSH, T4 or T3 or thyroid function not adequately controlled; or serum creatinine concentration  $\geq 1.5$  times upper limit of normal (ULN).
9. History or clinical evidence of any of the following:
  - a. variceal bleeding, ascites, hepatic encephalopathy, CTP score  $>6$ , decompensated liver disease or any other form of non-viral hepatitis
  - b. immunologically mediated disease (e.g. rheumatoid arthritis, inflammatory bowel disease, severe psoriasis, systemic lupus erythematosus) requiring more than intermittent non-steroidal anti-inflammatory medications for management or that requires frequent or prolonged use of corticosteroids (inhaled asthma medications are allowed)
  - c. any malignancy within 5 years except for basal cell skin cancer
  - d. significant or unstable cardiac disease (e.g. angina, congestive heart failure, uncontrolled hypertension, history of arrhythmia)
  - e. chronic pulmonary disease (e.g. chronic obstructive pulmonary disease) associated with functional impairment
  - f. severe or uncontrolled psychiatric disease, including severe depression, history of suicidal ideation, suicidal attempts or psychosis requiring medication and/or hospitalization
10. Patients with a body mass index of  $>30$  kg/m $^2$
11. Concomitant drugs known to prolong the QT interval
12. Concomitant use of immunosuppressive or immune modulating agents
13. Patients with any serious condition that, in the opinion of the investigator, would preclude evaluation of response or make it unlikely that the contemplated course of therapy and follow-up could be completed or increase the risk to the subject of participation in the trial

### **Summary of Dosing Plan/Treatment Plan/Schema**

At the Screening Visit, subjects giving written informed consent will have all required evaluations to determine their eligibility to participate in the study. The outpatient Screening Visit must occur within 21 days of first Study Visit.

Each eligible subject will undergo 8-19 Treatment Study Visits; Screening, Day 1, Day 2, Day 3, Day 7, Day 14, Day 28, then every 4 weeks (total treatment duration depends on assigned treatment group), followed by a Safety Follow-up Visit, 4 weeks post-treatment. Moreover, the investigator is free to initiate licensed medications at any time point and decrease the dose of EBP-994 if deemed warranted for GI side effects.

During the intervals between Study Visits, subjects will be free to carry on their usual activities of daily living. Subjects should be instructed to take the study medication at 24 (QD dosing), 12 (BID dosing) or 8 (TID dosing) hour intervals  $\pm$ 2 hours. Efforts should be made to schedule Study Visits according to the study protocol; however the window for consecutive Study Visits will be  $\pm$ 2 days with the exception of Days 2 and 3 for which a visit window is not allowed.

## **Criteria for Evaluation**

### **Statistical Plan**

The sample size has not been determined by strict statistical considerations. From a safety, pharmacokinetic and pharmacodynamic perspective, no a-priori assumptions are made as to the expected treatment effect and associated variability.

### **General**

Demographics of subjects will be described. All reported adverse events will be mapped to standard coding terms (MedDRA) and grouped by system organ class and preferred terms. The incidence of adverse events will be tabulated by seriousness, severity, and relationship to study drug. If an adverse event is reported more than once during the study period, the greatest severity and worst-case attribution will be presented in tables. Adverse events will also be listed for individual subjects, along with information regarding onset, duration, severity, and relationship to study drug. Adverse events that lead to withdrawal from the study will be listed and summarized by treatment group separately. Summary tables and listings of serious adverse events will also be generated. Pharmacodynamic data will be presented in listings and will display viral load data at each period/timepoint collected by subject. These data will also be presented graphically. Mean and median levels of the viral load will be calculated at each period/timepoint.

### **Safety**

Safety will be monitored by assessing vital signs, adverse events, concomitant medications and laboratory and ECG results. ECGs will be conducted in triplicate and vital signs assessed at each Study Visit.

The most common side effects seen with lonafarnib (the active ingredient of EBP-994) are gastrointestinal (diarrhea, nausea, and vomiting). There were no serious adverse events (SAEs) observed in the studies conducted in healthy volunteers. The SAEs reported in at least 2% of subjects in the Phase 1 and Phase 2 studies conducted in subjects with solid tumors or hematologic malignancies included fever (6%), diarrhea (6%), dehydration (6%), febrile neutropenia (4%) and sepsis (4%).

As with any anti-viral medication, a possible effect of EBP-994 is viral resistance. Hepatitis D viral load levels will be measured through quantitative PCR at all Study Visits. Viral mutation analysis and resistance phenotyping will be conducted to assess viral resistance to the study medication. The investigator may terminate the subject from the trial if, in his/her opinion, there is an unacceptable increase in HDV viral load. Moreover, the investigator is free to initiate standard of care (SOC) medications and doses (i.e. Pegasys®) at any time point.

### **Pharmacokinetics**

Blood samples will be obtained for pharmacokinetics of EBP-994 at Study Visit 1 (Day 1) and Study Visit 6 (Day 28). Pharmacokinetic parameters for EBP-994 such as maximum concentration ( $C_{max}$ ), area under the time-concentration curve (AUC), time to peak concentration ( $t_{max}$ ), elimination half life ( $t_{1/2}$ ), volume of distribution ( $V_{area/F}$ ) and clearance (CL/F)] will be calculated and tabulated with descriptive statistics. Geometric mean and geometric CV% will be provided for AUC and  $C_{max}$  values.

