### **8.5.1 PK Linearity and Accumulation Assessment**

The pharmacokinetic parameter  $AUC_{0-t}$  values will be compared against  $AUC_{inf}$  values using an analysis of variance (ANOVA) on the ln-transformed values for EBP-994. The ANOVA model will include Day (Day 1 ( $AUC_{inf}$ ) and Day 28 ( $AUC_{0-t}$ )) as fixed effects. The ANOVA will include calculation of least-squares means (LSM), the difference between day LSM and the standard error associated with this difference. The above statistical analysis will be done using the appropriate SAS® procedure.

*Ratio of LSM will be calculated using the exponentiation of the LSM from the analysis on the ln-transformed response. The ratio will be expressed as a percentage relative to  $AUC_{inf}$  (Day 1).*

Ninety percent confidence interval for the ratio will be derived by exponentiation of the confidence interval obtained for the difference between day LSM resulting from the analysis on the ln-transformed response. The confidence interval will be expressed as a percentage relative to  $AUC_{inf}$  (Day 1).

Accumulation will be evaluated by comparing the plasma exposure of EBP-994 on Day 28 ( $AUC_{0-t}$ ) to the exposure on Day 1 ( $AUC_{0-t}$ ).

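### The Day 28/Day 1 AUC model averages over regimens with and without Norvir, and no exposure comparison by Norvir status is planned although PK alone and in combination is a primary objective

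*Combined protocol and SAP*

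**What the plan says.** The Study Objectives in the Protocol Summary list as a primary objective: "Evaluate the safety, tolerability, PK, and HDV viral load of a treatment up to 48 weeks with EBP-994 alone and in combination with Norvir". The same objective also covers combinations that include Pegasys, and Section 2 repeats it. Four groups are randomised, two with Norvir (Groups 2 and 4) and two without (Groups 1 and 3). The caps on daily EBP-994 differ: Group 1 may go up to 600 mg, whereas the summary has "Group 2: EBP-994 (up to 200 mg daily dose) in combination with Norvir".

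The PK analysis is described in three places.

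- **Protocol Summary, Pharmacokinetics, and Section 8.5.** Parameters for Day 1 and Day 28 "will be calculated and tabulated with descriptive statistics". No grouping variable is named. Section 8.5 includes Day 1 CL/F, defined as dose over AUCinf, and does not report AUCinf for a profile without a terminal log-linear phase.
- **Section 8.5.1, ANOVA on ln AUC.** "The ANOVA model will include Day", with two levels: Day 1 (AUCinf) and Day 28 (AUC over the dosing interval). No other term is listed. The outputs are least-squares means, "the difference between day LSM and the standard error associated with this difference", and one ratio; "Ninety percent confidence interval for the ratio will be derived by exponentiation".
- **Section 8.5.1, accumulation.** "Accumulation will be evaluated by comparing the plasma exposure of EBP-994 on Day 28" with Day 1. No model, grouping or interval is given.

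PK sampling is optional (Section 3), and neither the size of the PK subset nor its split by Norvir status is stated. Section 8.7 makes no assumption about effects or variability.

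**The concern.** The design separates regimens by Norvir status and the objective asks for PK under each, but the only specified PK model ignores the distinction. Two things follow.

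First, the Day ratio is a weighted average over randomised regimens. Because PK participation is voluntary, the weights are set by who consents. If the ratio differs between regimens, the reported value describes neither and would shift with the make-up of the volunteers.

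Second, no analysis says how EBP-994 exposure with Norvir relates to exposure without it. Any such statement for this primary objective would be chosen after the data are seen.

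**Working it through.** There is no stated figure to reproduce. The first step is a reading of the text; the rest are illustrations on assumed inputs.

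**1. What is specified by regimen.**

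| Item | Grouping or regimen term stated |
|---|---|
| PK tables (Protocol Summary, 8.5) | None named |
| Day ANOVA (8.5.1) | Day only; no Norvir, group, dose or subject term |
| Accumulation (8.5.1) | None named; no model |
| Exposure with versus without Norvir | Not planned |
| Adverse events leading to withdrawal (8.4.1) | By treatment group |

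**2. What the Day-only model estimates.** Let p be the share of PK subjects on Norvir, and r0 and r1 the true Day ratios without and with it. With complete data, the difference of day means on the ln scale is (1 − p) ln r0 + p ln r1, so the pooled ratio is r0^(1 − p) × r1^p. Set r0 = 1.0 and vary r1 (all values assumed):

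| r1 | p = 25% | p = 50% | p = 75% |
|---|---|---|---|
| 0.70 | 0.91 | 0.84 | 0.77 |
| 1.25 | 1.06 | 1.12 | 1.18 |
| 1.5 | 1.11 | 1.22 | 1.36 |
| 2.0 | 1.19 | 1.41 | 1.68 |

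The last row is 2^0.25, 2^0.5 and 2^0.75. If r1 = r0, the formula returns the common ratio for any p, so pooling then causes no bias.

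**3. Unequal loss of Day 1 AUCinf.** Sampling stops at 12 h (Sections 6.2 and 6.7), and AUCinf is withheld where no terminal phase is seen. Suppose both true ratios are 1.0, exposure with Norvir is R times that without, and a share m of Norvir subjects lose Day 1 AUCinf. The Norvir share on Day 1 becomes p1 = p(1 − m) / [p(1 − m) + 1 − p], and the Day-only ratio becomes R^(p − p1).

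- p = 0.5, m = 0.5: p1 = 0.25/0.75 = 1/3. R = 2 gives 2^(1/6) = 1.12; R = 3 gives 3^(1/6) = 1.20.
- p = 0.5, m = 1: p1 = 0. R = 2 gives 1.41; R = 3 gives 1.73.

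This distortion arises because the model has no subject or Norvir term, so the two day means come from different mixes of people.

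**4. Precision of the pooled ratio.** Treat the two days as independent, as the model is written. With 20 subjects, half on Norvir, and a within-group CV of 40% (assumed), the 90% CI is the estimate multiplied and divided by exp(t × SE). With Day only, SE = √[ln(1.16) + 0.25 (ln R)²] × √(2/20), giving a factor of 1.32 at R = 2 and 1.43 at R = 3. With a group term it is 1.23.

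**5. Is the missing comparison estimable?** For a geometric mean ratio with n subjects per side, the 90% CI factor is exp(t × s × √(2/n)), with s² = ln(1 + CV²) and 2n − 2 degrees of freedom. For n = 10 and CV 30%: s = 0.294, SE = 0.131, t = 1.734, factor 1.26.

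| n per side | CV 30% | CV 50% |
|---|---|---|
| 6 | 1.36 | 1.64 |
| 10 | 1.26 | 1.44 |
| 18 | 1.18 | 1.31 |
| 37 | 1.12 | 1.20 |

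The last row corresponds to nearly all of the up to 75 subjects consenting and splitting evenly. A useful estimate is within reach at modest numbers.

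**The case against.** The strongest reply is that much of this is silence rather than error. The tables could be produced by group without breaking any sentence of the plan. The accumulation comparison is a second Day 28/Day 1 analysis, and nothing says it is pooled. Day 1 CL/F is planned and is the inverse of dose-normalised exposure, so the raw material for judging Norvir is already there. Subjects start their assigned regimen on Day 1, so both PK days normally fall under the same assignment: the mixing is between subjects, and bias needs a Norvir-by-Day difference or unequal loss of AUCinf. The study is a pilot, and the combination objective asks for evaluation, whereas the dose objectives set 200 mg against 300 mg.

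All of that stands, and it rules out several stronger readings. A reader might infer that all PK results are pooled; only the ANOVA is explicitly so. A reader might infer that the effect of Norvir can never be estimated; the documents show only that no estimate is planned. A reader might take the dose caps as proof that the sponsor expects different exposure per mg with Norvir. But Section 6.2 caps Group 3, which has no Norvir, at 200 mg, while the Protocol Summary gives it 600 mg, so the caps do not separate cleanly by Norvir status. The documents name CYP3A as the metabolic route of EBP-994 but do not say what Norvir does to it, so an effect of Norvir that builds up between Day 1 and Day 28 is an assumption.

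The reply does not reach the stated Day-only model or the absence of any comparison by Norvir status. The pilot argument supports labelling that comparison exploratory, not leaving it out.

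**Conclusion.** The point holds in this form: the one specified PK model averages over regimens, the accumulation analysis and tables leave grouping open, and the Norvir comparison relevant to a primary objective is not planned. It should be corrected before the data are analysed.

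The size is conditional. With assumed Day ratios of 1.0 and 2.0, the pooled value runs from 1.19 to 1.68 as the Norvir share goes from 25% to 75%. With equal ratios and complete AUCinf the bias is nil, although precision may still suffer. It would be too strong to say that the ratio must be wrong or describes no regimen. The missing comparison depends on none of these assumptions.

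**What to change.** - **Section 8.5.1, ANOVA.** Add Norvir (yes/no), Norvir by Day, and subject. Fitting subject as a random effect keeps the Norvir main effect estimable. Report the Day 28/Day 1 ratio with 90% CI separately with and without Norvir.
- **Section 8.5.1, accumulation.** State the same model for the accumulation ratio, and report it with 90% CI by Norvir status.
- **Section 8.5.** Tabulate PK parameters by randomised group and by EBP-994 dose, with the number of subjects who have a reportable Day 1 AUCinf. This also keeps the Pegasys groups and the 200 and 300 mg twice-daily doses visible, which a Norvir stratum alone would still mix.
- **New exploratory contrast.** Geometric mean ratio of dose-normalised Day 28 AUC and Cmax, with versus without Norvir, with 90% CI. State that it assumes dose proportionality, because Norvir status goes with different dose caps.
- **First, reconcile the caps.** The Protocol Summary and Section 6.2 disagree for Group 3 (600 versus 200 mg daily) and Group 4 (150 versus 200 mg daily).

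The cost is SAP wording and programming; no new samples, visits or subjects are needed. The downsides are wider intervals within each stratum than an analysis of all subjects together would give under the same model, and a Norvir contrast that rests on dose proportionality.

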### **Pharmacodynamics**

Mean and median levels of the viral load will be calculated.

### **Estimated Start and Completion Dates**

[figure not shown]
July 2013 through July 2017.

## 1 BACKGROUND

Hepatitis D virus (HDV) was first described as a novel antigen in the nucleus of hepatocytes derived from patients infected with hepatitis B (HBV) and antibodies to this “delta antigen” were detected in patients with severe cases of HBV infection. HDV was subsequently identified as the infectious agent causing viral hepatitis in the presence of HBV (1,2). While HDV can replicate autonomously (3), the virus does require co-infection with HBV to complete virion assembly and to facilitate transmission. HDV uses the hepatitis B surface antigen (HBsAg) proteins L, M, and S, as its envelope protein which is pivotal for HDV exit from host cells and transmission to other hepatocytes (4). Therefore, HDV can be considered a superinfection among patients chronically infected with HBV or as a simultaneous acute co-infection with HBV (5).

The HDV genome is a small circular single-stranded RNA molecule which can be classified into eight different genotypes (6). HDV genotype 1 is the most prevalent globally and is the most common in Europe and North America. The main route of transmission is parenteral exposure, like that observed with HBV. In the United States, the number of cases of HDV is projected to be roughly 40,000 to 75,000, or 5% of the estimated 750,000 to 1.5 million persons infected with HBV (14). Multiple studies have revealed that chronic HDV infection leads to more severe liver disease than HBV mono-infection, is associated with accelerated fibrosis progression, as well as a higher risk of developing hepatocellular carcinoma (7,8,9). HDV is the only form of chronic viral hepatitis for which there is no established highly successful treatment. Despite multiple direct antiviral agents directed against HBV, these have not proven effective against HDV, nor has ribavirin alone, or in combination with interferon (10,11,12,13)

Given the aggressive nature of the hepatitis seen in HDV infection, agents are needed that can help mitigate the disease by directly interfering with the virus life-cycle. An important interaction between HDV and HBV proteins has been shown to depend on the presence of the last four amino acids of the large delta antigen, comprising a CXXX box motif, where C represents cysteine and X denotes any other amino acid. This amino acid sequence is required for the protein to be post-translationally modified by farnesyltransferase (FT), an enzyme which covalently attaches a prenyl lipid (farnesyl) to the cysteine of the CXXX box as depicted in Figure 1 (15,16). Prenylation of HDV results in the addition of farnesyl to the delta antigen. Inhibiting the action of FT could result in compromised HDV particle production since the unprenylated large delta antigen of HDV cannot associate with HBV antigens to form an infective HDV virion. In addition, the use of FT inhibitors (FTIs) could subvert the ability of the virus to develop resistance since the drug targeted locus does not lie within the viral genome but is a host function. Most importantly, host cells display a tolerance in the presence of prenylation inhibition by FTIs through the use of alternative prenylation pathways while HDV cannot use alternative pathways (17,18).

**Figure 1** The Mevalonate Pathway

Eiger BioPharmaceuticals, Inc. (Eiger BioPharmaceuticals) is developing EBP-994 as an investigational new drug for the treatment of hepatitis D virus (HDV) in patients chronically infected with HDV. EBP-994 is an orally active tricyclic farnesyltransferase inhibitor (FTI) initially developed as lonafarnib (aka SCH 66336) by Schering-Plough, now Merck. It has been studied in over 2000 patients within the context of over a dozen clinical studies, including three Phase I (pharmacokinetic, metabolic distribution, drug-drug interaction) healthy volunteer studies and nine Phase I, II and III studies in patients with advanced malignancies in an attempt to inhibit farnesylated ras-mediated cancers. In patients with advanced cancers (blast crisis and acute leukemia), EBP-994 has been given for up to 120 days with the MTD determined to be 200-300 mg PO BID, with TEAEs being diarrhea and nausea.

[figure not shown]
The drug was generally well tolerated, although insufficient anti-tumor efficacy was observed, likely because such malignancies can be driven by additional factors beyond farnesylated ras. EBP-994 offers a valuable repurposing opportunity, however, for inhibiting the HDV life cycle where a critical dependence on farnesylation of large delta antigen has been demonstrated, and thereby treating hepatitis D infections.

